2.3 RISK/BENEFIT ASSESSMENT

The presence of a DFU incurs certain risks. Compared to people with diabetes alone, those with diabetes and a foot ulcer have a 9-fold greater risk for developing an infection, a 7-fold greater risk of amputation, a 3.5-fold greater risk of a fracture and are more than twice as likely to fall.¹⁹ The longer the ulcer is open, the greater the chance for infection and amputation.²⁰ Thus, the focus of care of the DFU is to close the wound as quickly as possible.

2.3.1 KNOWN POTENTIAL RISKS

AMNIOEXCEL Plus

AMNIOEXCEL Plus is intended for use as a wound covering. This product is an allograft tissue intended for homologous use for the repair, reconstruction, and replacement of skin at the direction of a physician.

AMNIOEXCEL Plus contains trace amounts of ethanol. It should be not used in patients with known sensitivity to ethanol.

In order to reduce the risk of complications, AMNIOEXCEL Plus should not be used in the presence of active infection.

Although donor tissue is evaluated and processed following strict FDA guidelines, the donor screening methods are limited and may not detect all diseases. As with any allograft, complications at the graft site may occur post-operatively (i.e., post-application) that are not readily apparent. These include, but are not limited to:

- Transmission of communicable diseases, including those of unknown etiology
- Transmission of infectious agents such as viruses, bacteria, and fungi
- Immune reaction of, or allergic reaction to, implanted HCT/P

Apligraf

Apligraf is indicated for use with standard DFU care for the treatment of full-thickness neuropathic DFUs of greater than three weeks' duration which have not adequately responded to conventional ulcer therapy and which extend through the dermis but without tendon, muscle, capsule or bone exposure.

The following are adverse events (AEs) reported in greater than 1.0% of Apligraf patients in a DFU study conducted by the manufacturer.

10-20% of Subjects

- Neuropathic ulcer (non-study site)
- Suspected wound infection (non-study site)
- Non-neuropathic skin alteration (non-study site)
- Suspected wound infection (study site)

5-10% of Subjects

- Cellulitis (non-study site)
- Cellulitis (study site)
- Osteomyelitis (non-study site)
- Vesicular bullous rash (non-study site)
- Pain (overall body)
- Fungal infection (non-study site)
- Hypoglycemia
- Infection (overall body)
- Hematoma (non-study site)

<5% of Subjects

- Deteriorating ulceration (study site)
- Rash (non-study site)
- Non-neuropathic skin alteration (study site)
- Pain (non-study site)
- Bone dislocation (non-study site)
- Peripheral edema
- Accidental Injury (overall body)
- Accidental Injury (non-study site)
- Fever (overall body)
- Hyperglycemia
- Dry skin (non-study site)
- Chest pain
- Bronchitis
- Osteomyelitis (study site)
- Nausea
- Pharyngitis
- Anemia
- Right Heart failure
- Abscess (study site)
- Urinary tract infection
- Deteriorating ulceration (non-study site)
- Gastroenteritis
- Cataract
- Abscess (overall body)
- Gastritis
- Spontaneous bone fracture
- Diarrhea
- Positive Wound Culture (study site)
- Arthrosis (non-study site)
- Malaise
- Rash (study site)
- Hematoma (study site)
- Gangrene (non-study site)
- Dyspepsia
- Accidental Injury (study site)
- Infection (non-study site)
- Gangrene (study site)
- Spontaneous bone fracture (non-study site)
- Viral infection
- Back pain
- Angina pectoris
- Arteriosclerosis
- Cardiomegaly
- Gastrointestinal carcinoma
- Colitis
- Rhinitis
- Arthritis
- Confusion

Apligraf is contraindicated for use on clinically infected wounds.

Apligraf is contraindicated in patients with known allergies to bovine collagen.

Apligraf is contraindicated in patients with a known hypersensitivity to the components of the Apligraf agarose shipping medium listed below:

- agarose,
- L-glutamine,
- hydrocortisone,
- human recombinant insulin,
- ethanolamine,
- O-phosphorylethanolamine,
- adenine,
- selenious acid,
- DMEM powder,
- HAM's F-12 powder,
- sodium bicarbonate,
- calcium chloride

Standard of Care (SOC) Treatment

SOC consists of: 1) moist wound dressings, 2) debridement of necrotic/non-viable tissue, 3) infection surveillance and management and 4) offloading of weight bearing from vicinity of the ulcer.

In this study, the moist wound dressings include normal saline gel which is then covered with a non-adhesive foam and secured with conforming roller gauze and dressed with Coban.

The risks of SOC procedures are as follows:

Use of Wrap and Bandages

Tightness - Some subjects may experience a sense of tightness after the study doctor or staff apply the bandages over the treatment area.

Contact Dermatitis - Some subjects may experience a localized skin reaction to the bandages

Use of the offloading boot

Imbalance – Some subjects may have initial or long-term difficulty walking with the offloading boot.

Restriction of activities/movement – Some subjects may experience an inability or reduction in ability to do things that they were once able to do (i.e., wear shoes on the foot, ambulate, etc.)

Debridement Procedure

The risks associated with the debridement procedure are as follows:

- Pain - Most patients will experience pain either during or after the debridement procedure.
- Bleeding – Most patients will experience bleeding of the ulcer after debridement
- Infection - Few patients will develop an infection after debridement
- Delayed Healing - Few patients will develop delayed healing of the ulcer after debridement
- Loss of Healthy Tissue – Few patients will experience removal of healthy tissue in addition to removal of dead tissue.

Reaction to topical or local anesthesia (if used) – Few patients will experience a reaction to topical or local numbing agents used to decrease pain prior to debridement.

Hemoglobin A1c Test (Finger stick or Blood Draw)

The risks associated with the hbA1c procedure are as follows:

- pain
- bruising
- dizziness
- infection

Vascular Perfusion Tests

Risks of Measuring the Ankle-Brachial Index

- Pressure/Discomfort around the arm and/or the leg – Most subjects who have this test performed will experience pressure and discomfort from the blood pressure cuff that is applied to either the leg or arm.
- Bruising – Some subjects may experience bruising from the blood pressure cuff

Risks of Taking Toe Pressure

- Pressure/Discomfort around the big toe – Some subjects who have this test performed will experience pressure and discomfort from the cuff.

Risks of Measuring Transcutaneous Oximetry

- Contact Dermatitis - Some subjects may experience a localized skin reaction to the gel used with the probes that will be applied to the skin for this test.

2.3.2 KNOWN POTENTIAL BENEFITS

A recent meta-analysis noted that some patients who use tissue-based allografts heal sooner than those who undergo SOC procedures alone.¹³ However, because this is the first clinical trial using AMNIOEXCEL Plus in the management of DFUs, improved outcome for subjects in this group cannot be guaranteed.

Subjects in this study may undergo more rigorous and/or more frequent treatments compared to their non-study counterparts. This may assist in the entire study population's prognosis, although it cannot be guaranteed.

[Intentionally Blank]

3 OBJECTIVES AND ENDPOINTS

Table 3: Objectives and Endpoints

OBJECTIVES	ENDPOINTS
Primary	
The primary objective of this study is to compare outcomes associated with the use of AMNIOEXCEL Plus Placental Allograft Membrane, Apligraf living, bi-layered skin substitute and SOC in the management of DFUs.	The primary endpoint of this study is the incidence of complete wound closure, as assessed by the Investigator at or before Week 12 of the Treatment Phase and confirmed 2 weeks later. Confirmed complete wound closure is defined as complete skin re-epithelialization that is without drainage or dressing requirements.
Secondary	
1. Determine the proportion of subjects in each study arm with complete closure of the study ulcer at or before 12 weeks of treatment	1. Proportion of subjects with complete closure of the study ulcer at or before Week 12 and confirmed 2 weeks later as assessed by computerized planimetry. 2. Proportion of subjects with complete wound closure of the study ulcer at or before Week 12 and confirmed 2 weeks later as assessed by independent, blinded, assessment of photographs.
2. Determine the time to complete wound closure in each study arm	1. Time to complete wound closure, as assessed by the Investigator. 2. Time to complete wound closure, as assessed by computerized planimetry.
3. Determine the rate of wound closure in each study arm	1. Rate of wound closure, as assessed by computerized planimetry.
4. Assess medical resource utilization outcomes in each study arm	1. Medical resource utilization associated with treatment of DFU and related complications as determined by a comparison of estimated costs from the presumed billing codes which would have been used for each patient.
Exploratory	
1. The proportion of subjects in each cohort whose wounds are closed at 4 weeks of treatment.	1. Wound closure status at Week 4 of Treatment
2. The effect of any covariate on the primary endpoint.	1. Co-variate analyses of the primary endpoint using those listed in section 9.3.
Safety Endpoints	
The safety objective of this study is to assess adverse events associated with either of the study treatments and/or all study procedures in the management of DFUs.	Incidence of all treatment, procedure, and/or wound-related adverse events or serious adverse events in any of the study cohorts.

4 STUDY DESIGN

4.1 OVERALL DESIGN

This is a prospective, multicenter, parallel-group, randomized, three-arm trial designed to assess the proportion of ulcers achieving complete wound closure and confirmed 2 weeks later in a population with adequate arterial circulation, following up to 11 weeks of either AMNIOEXCEL Plus Placental Allograft Membrane with SOC, Apligraf bi-layered skin substitute with SOC, or SOC alone.

Subjects will be randomized 1:1:1 to receive one of the following:

- AMNIOEXCEL Plus Placental Allograft Membrane with SOC
- Apligraf bi-layered skin substitute with SOC
- SOC alone

4.2 SCIENTIFIC RATIONALE FOR STUDY DESIGN

Prospective, multicenter, randomized studies provide the most objective methods for analyzing the outcomes of multiple treatment groups. The use of a three-cohort study allows simultaneous comparison of the treatment in question utilizing an active comparator and current SOC, the true baseline.

4.3 JUSTIFICATION FOR INVESTIGATIONAL PRODUCTS/TREATMENTS

While there may be generalizable evidence that all tissue-based allografts outperform SOC therapies in the management of DFUs, the performance of specific products varies. Although there is evidence that AMNIOEXCEL Amniotic Allograft Membrane outperforms SOC procedures^{1,21-23}, AMNIOEXCEL Plus Placental Allograft Membrane has not been assessed as an advanced wound therapy for DFUs.

The comparator treatment, Apligraf, has been investigated as an advanced treatment for patients with DFUs and has been compared to SOC procedures.^{3,18,24}

The use of an offloading boot is a known and widely used SOC adjunctive therapy. Clinical studies have shown that offloading with rigid boots provide a more aggressive healing rate as compared to shoes, custom insoles, wheelchairs, bedrest, and/or crutches.²⁵ The use of a boot in this clinical trial, in addition to moist wound dressings, will provide the most robust baseline to compare the active treatments (i.e., Investigational products) against.

4.4 END OF STUDY DEFINITION

The study is considered completed after all of the screened and enrolled (i.e., randomized) subjects have completed all of their study treatments and been signed off by the investigative sites in the electronic data capture (EDC) system.

5 STUDY POPULATION

5.1 INCLUSION CRITERIA

All of the following criteria must be met by a potential subject to be enrolled in the study. The subject must:

1. Have participated in the informed consent process and signed a study-specific informed consent document.
2. Be able and willing to comply with study procedures, including study visits, study dressing regimens, and compliance with study required offloading device.
3. Be ≥ 21 years of age.
4. Have Type I or Type II diabetes mellitus with Investigator-confirmed glycosylated hemoglobin (HbA1c) of $\leq 12\%$ within 3 months prior to screening visit.
5. Have at least one diabetic foot ulcer that meets ALL of the following criteria:
 - Ulcer has been in existence for a minimum of four weeks prior to signing the Informed Consent Form for trial participation but no more than 12 months
 - Ulcer is a partial or full thickness diabetic foot ulcer without capsule/tendon/bone exposure (Wagner Grade 1 or superficial 2).
 - Ulcer is located on the foot or ankle (with no portion above the top of the malleolus, i.e., proximal to the malleolus).
 - If the subject has more than one ulcer that meets the eligibility criteria, the ulcer designated as the study ulcer will be at the discretion of the Investigator.
 - There is a minimum 1 cm margin between the qualifying study ulcer and any other ulcer on that same foot, post-debridement.
6. Ulcer size (i.e., area) is $\geq 1 \text{ cm}^2$ and $\leq 12 \text{ cm}^2$ post-debridement at Screening Visit 1 and Randomization (Day 0).
7. Have adequate vascular perfusion of the affected limb as defined by **at least one** of the following:
 - Ankle-Brachial Index (ABI) ≥ 0.65 or ≤ 1.2 , performed *within 3 months* of screening visit 1
 - Toe pressure (plethysmography) $>50 \text{ mmHg}$ *at time* of screening visit 1,
 - $\text{TcPO}_2 >40 \text{ mmHg}$ *at time* of screening visit 1
8. Be willing and able (or have a family member/friend willing and able) to apply required applicable dressing changes as well as study-required offloading/protective device if and when applicable.

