
Inclusion Criteria
	
All of the following criteria must be met by a potential subject to be enrolled (i.e., randomized) in the study. The subject must:
 
 1. Have participated in the informed consent process and signed a study-specific informed consent document. 2. Be able and willing to comply with study procedures, including study visits, study dressing regimens, and compliance with study required offloading device. 3. Be ≥ 21 years of age. 4. Have Type I or Type II diabetes mellitus with Investigator-confirmed glycosylated hemoglobin (HbA1c) of $\leq 12\%$ within 3 months prior to screening visit. 5. Have at least one diabetic foot ulcer that meets ALL of the following criteria: 
 • Ulcer has been in existence for a minimum of four weeks prior to signing the Informed Consent Form for trial participation but no more than 12 months • Ulcer is a partial or full thickness diabetic foot ulcer without capsule/tendon/bone exposure (Wagner Grade 1 or superficial 2). • Ulcer is located on the foot or ankle (with no portion above the top of the malleolus, i.e., proximal to the malleolus). • If the subject has more than one ulcer that meets the eligibility criteria, the ulcer designated as the study ulcer will be at the discretion of the Investigator. • There is a minimum 1 cm margin between the qualifying study ulcer and any other ulcer on that same foot, post-debridement. 6. Ulcer size (i.e., area) is $\geq 1 \text{ cm}^2$ and $\leq 12 \text{ cm}^2$ post-debridement at Screening Visit 1 and Randomization (Day 0). 7. Have adequate vascular perfusion of the affected limb as defined by at least one of the following (in order of preference): 
 • Ankle-Brachial Index (ABI) ≥ 0.65 and ≤ 1.2, performed within 3 months of screening visit 1 • Toe pressure (plethysmography) $>50 \text{ mmHg}$ at time of screening visit 1, • $\text{TcPO}_2 >40 \text{ mmHg}$ at time of screening visit 1 8. Be willing and able (or have a family member/friend willing and able) to apply required applicable dressing changes as well as study-required offloading/protective device if and when applicable.

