8.1.1 SCREENING VISIT 1 (-2 WEEKS [14 DAYS] ± 3 DAYS)

1. Conduct Informed Consent Process (Informed Consent & HIPAA)
2. Review Eligibility Criteria (Inclusion/Exclusion)
3. Collect Demographics & Medical History from Patient
4. Perform Physical Examination
5. Perform Vascular Perfusion Assessment (if most recent ABI is greater than 3 months old or no assessment is present in subject's medical records)
 - a. ABI, Toe Pressure, or TcPO₂ (ABI is preferred)
6. Discuss Requirements for Study Compliance (Treatment Compliance Review)
7. Perform Sharp Debridement on Study Ulcer, if needed (Debridement)
8. Collect Images of the DFU (Photography)
9. Perform Ulcer Assessments
10. Treat Subject Using SOC Procedures (Standard of Care)
11. Train subject on wound cleansing and dressing changes
12. Apply Boot, if applicable (Boot Application)
13. Document Concomitant Medications & Procedures (ConMeds and Other Procedures)

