Subjects enrolled in this study must have an ABI of between 0.65 and 1.2. NOTE: An ABI result obtained within 3 months of the first screening visit may be used to qualify the potential subject for participation in this study.

- **Toe Pressure**
The blood pressure within the toe is measured in much the same way as obtaining blood pressure in the arm. Briefly, use a Doppler probe to determine that a pulse is present at the base of the great toe. Apply the correct sized cuff to the great toe and place the Doppler probe distal to the cuff (the pulse should be audible). Inflate the cuff sufficiently to occlude the pulse and slowly release the cuff. Note the pressure, in mmHg, when the pulse returns. To participate in this study, the potential subject must have a toe pressure greater than 50mmHg in the foot with the study ulcer.
- **Transcutaneous Oxygen Level (TcPO₂)**
TcPO₂ is a measure of oxygen delivery to a local area. A special machine must be used to assess TcPO₂. Briefly, electrodes for the sensor will be placed onto the intact skin close to the study ulcer. The oxygen sensor then can read the oxygen content of the tissue and reports this as mmHg pressure. Each site should refer to the equipment's manual for specific and correct instructions for use. For this study, potential study candidates must have a TcPO₂ greater than 40 mmHg.
- **Treatment Compliance Review (Screening Visit 1 & 2, Randomization, Weeks 1 - 12)**
Screening Visits 1 & 2: The site will instruct the subject on how to perform daily dressing changes and apply the offloading boot, if offloading is used.

Randomization Visit: For subjects randomized to the SOC cohort, the site will instruct the subject on how to perform daily dressing changes and apply the offloading boot, if offloading is used. For those subjects randomized to the AMNIOEXCEL Plus or Apligraf cohorts, only the offloading boot will be discussed, if applicable. Subjects in these arms do not change their dressings at home.

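### Section 5.1 words the ABI limits so that every ABI meets them, contradicting the synopsis and Section 8.2 and leaving eligibility and per-protocol status unclear for some subjects

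*Protocol*

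**What the plan says.** The ABI limits appear in three places in the Protocol.

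- Section 5.1, inclusion criterion 7: "Ankle-Brachial Index (ABI) ≥ 0.65 or ≤ 1.2", performed within 3 months of Screening Visit 1.
- Synopsis (Section 1), inclusion criterion 7: "Ankle-Brachial Index (ABI) ≥ 0.65 and ≤ 1.2", with the same time window.
- Section 8.2, vascular perfusion assessment: "Subjects enrolled in this study must have an ABI of between 0.65 and 1.2".

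In the synopsis and in Section 5.1, criterion 7 begins "Have adequate vascular perfusion of the affected limb as defined by" and is met by at least one of three tests: ABI, toe pressure above 50 mmHg, or TcPO2 above 40 mmHg. The synopsis adds that the tests are listed in order of preference. Sections 8.1.1 and 8.2 name ABI as the preferred test. Section 8.1.1 calls for a perfusion assessment only when the latest ABI is more than 3 months old or no assessment is on record. Section 4.1 describes the trial as conducted "in a population with adequate arterial circulation".

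**The concern.** Criterion 7 is the only inclusion or exclusion criterion that puts a numerical limit on perfusion, and ABI is the preferred way to meet it. If the ABI part cannot fail, toe pressure and TcPO2 cannot exclude anyone with an in-window ABI, because one passing test is enough.

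Under Section 8.2, sites record in the EDC whether each criterion is met. Under Section 10.1.8.1, randomization follows only when all are met. A site working from Section 5.1 could record criterion 7 as met for an ABI that the synopsis and Section 8.2 put out of range.

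Two things are at stake. The first is whether the randomized population matches the design statement. Section 2.2 treats adequate perfusion as a condition for timely healing, yet perfusion is not among the candidate covariates in Protocol 9.3 or SAP 9, and Section 6.3 describes no stratification by it. The second is the per-protocol set, which Protocol 9.3 and SAP 8.2 define by the absence of a major protocol violation. If the protocol contradicts itself on eligibility, membership cannot be settled for the subjects affected.

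**Working it through.** The plan gives no figure to reproduce. The check is one of logic.

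**Step 1: the ABI limits alone.** The inputs are the limits 0.65 and 1.2 and the word that joins them.

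- With *or*: the set of x with x ≥ 0.65 or x ≤ 1.2. Since 0.65 < 1.2, the two half-lines overlap and together cover every number.
- With *and*, or *between*: the set 0.65 ≤ x ≤ 1.2.

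A grid from 0.000 to 3.000 in steps of 0.001 has 3001 values. With *or*, 3001 of 3001 pass. With *and*, (1.200 − 0.650)/0.001 + 1 = 551 pass. These counts describe a number line, not a share of subjects.

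| ABI | *or* (Section 5.1) | *and* / *between* (synopsis, Section 8.2) |
|---|---|---|
| 0.20 | passes | fails |
| 0.64 | passes | fails |
| 0.65 | passes | passes |
| 0.90 | passes | passes |
| 1.20 | passes | passes |
| 1.21 | passes | fails |
| 2.00 | passes | fails |

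**Step 2: the whole criterion.** The *at least one of three* rule and the 3-month window now come in.

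| Recorded tests | Section 5.1 alone | Synopsis | Section 8.2 ABI sentence, literally |
|---|---|---|---|
| ABI in range | met | met | met |
| ABI out of range, no other qualifying test | **met** | **not met** | **not met** |
| ABI out of range, toe pressure or TcPO2 qualifies | met | met | not met |
| No in-window ABI, toe pressure or TcPO2 qualifies | met | met | not met |
| No in-window ABI, no other qualifying test | not met | not met | not met |

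The second row is the main contradiction. The third and fourth rows are a separate one: Section 8.2 says enrolled subjects must have an in-range ABI, while the synopsis and Section 5.1 let another test stand in. Section 8.2 itself asks for only one of the three tests and uses similarly mandatory wording for toe pressure and TcPO2, so the sentence may be meant only for subjects assessed by ABI. The text does not say so.

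**Step 3: consequence for the analysis sets.** Protocol 10.1.9 defines a deviation as any noncompliance with the protocol. A subject in the second row complies with Section 5.1 and not with the synopsis or Section 8.2. No rule says which text decides, so deviation status, and with it per-protocol membership, is open. With 38 subjects per arm, one subject's outcome moves an arm's ITT closure rate by 1/38, about 2.6 percentage points, if all 38 are in the denominator.

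**The case against.** The strongest reply is that this is a drafting slip whose intent is plain. Two of the three statements give a closed range, and one of them, Section 8.2, is in the protocol body where the test itself is described. Many sites would probably infer a range. Exclusion 8 removes suspected or confirmed gangrene of the study ulcer. Exclusion 15 removes, in the Investigator's opinion, non-diabetic conditions that could interfere with healing. SAP 10.8 already summarizes the vascular perfusion assessments.

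Much of this stands, and it rules out three stronger readings that a reader might infer.

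- *That the perfusion criterion excludes nobody who has an ABI.* This would need Section 5.1 to override the synopsis and Section 8.2, and nothing in the documents says that it does. Even on the Section 5.1 text, the ABI must fall within the 3-month window.
- *That a site could randomize a subject on an out-of-range ABI alone without a deviation.* Doing so would still conflict with Section 8.2 and the synopsis. Its deviation status is disputed, not clear.
- *That the error changed the population or the closure rates.* The documents do not show how sites or the EDC applied the criterion, or that any out-of-range subject was enrolled. Under the synopsis, too, an out-of-range ABI is not disqualifying if toe pressure or TcPO2 qualifies.

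The contradiction itself remains. The two exclusions set no numerical perfusion limit. The opening words of criterion 7 add no independent standard, because they define adequate perfusion by the listed tests. A descriptive summary of perfusion values does not classify anyone as eligible or as a deviation.

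**Conclusion.** The point holds as an internal contradiction in a stated eligibility threshold. Read alone, the ABI limits in Section 5.1 are met by every in-window ABI, and that satisfies the whole criterion. The synopsis and Section 8.2 state a two-sided range. Section 8.2 also conflicts, on its face, with the option to qualify by toe pressure or TcPO2.

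The subjects whose eligibility, deviation status and per-protocol membership are ambiguous on the main contradiction are those with an in-window ABI outside 0.65 to 1.2 and no other qualifying test. Their number is not shown and could be zero. The conclusion assumes only that the three passages carry equal authority, since no order of precedence is given. It takes no position on which limits or which rule is clinically right.

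**What to change.** 1. The sponsor reconciles the synopsis, Section 5.1 and Section 8.2 into one perfusion rule and repeats it in the same words in all three places. The rule should state how the two ABI limits combine, whether an in-range ABI is required of everyone, and how an out-of-range ABI is treated when toe pressure or TcPO2 qualifies.
2. List ABI (with date), toe pressure and TcPO2 for every randomized subject and check them against the reconciled rule. Because the protocol asks for only one test, a subject entered on an out-of-range ABI may have no second test on record. The rule should say how that case is classified.
3. Classify the resulting deviations, and say which are major, before the per-protocol set is fixed. Record the rule in the SAP next to the per-protocol definition.

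The cost is a short amendment and one listing covering the planned 114 subjects. SAP Section 12 describes the independent photograph review as already done, which suggests that data collection was well advanced. If enrolment is over, the amendment can no longer affect who enters, and steps 2 and 3 are the part that still matters.
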